6.3 Lifestyle Restrictions

6.3.1 Meals and Dietary Restrictions

Participants should maintain a normal diet unless modifications are required to manage an AE such as diarrhea, nausea, or vomiting.

6.3.2 Contraception

Pembrolizumab may have adverse effects on a fetus *in utero*. Furthermore, it is not known if pembrolizumab has transient adverse effects on the composition of sperm.

Developmental and reproductive toxicity studies have not been performed with epacadostat. Epacadostat should not be used by pregnant women.

Participants should be informed that taking the study treatment may involve unknown risks to the fetus (unborn baby) if pregnancy were to occur during the study. In order to participate in the study, participants of childbearing potential must adhere to the contraception requirement (described above in Section 6.1 Inclusion Criteria) from the day of study treatment initiation (or 14 days prior to the initiation of study treatment for oral contraception) throughout the study period up to 120 days after the last dose of study treatment. If there is any question that a

participant of childbearing potential will not reliably comply with the requirements for contraception, that participant should not be entered into the study.

Definitions of WOCBP and standards for adequate contraception are outlined in Appendix 5.

6.3.3 Pregnancy

If a participant becomes pregnant while on treatment with pembrolizumab and/or epacadostat, the participant will be immediately discontinued from study treatment. The site will contact the participant at least monthly and document the participant's status until the pregnancy has been completed or terminated. The outcome of the pregnancy will be reported to the MSD without delay and within 24 hours if the outcome is a serious adverse experience (eg, death, abortion, congenital anomaly, or other disabling or life-threatening complication to the mother or newborn). The study Investigator will make every effort to obtain permission to follow the outcome of the pregnancy and report the condition of the fetus or newborn to MSD. If a male participant impregnates his female partner, the study personnel at the site must be informed immediately and the pregnancy must be reported to MSD and followed as described in Section 9.3.6.

6.3.4 Use in Nursing Women

It is unknown whether pembrolizumab or epacadostat is excreted in human milk. Since many drugs are excreted in human milk, and because of the potential for serious adverse reactions in the nursing infant, participants who are breastfeeding are not eligible for enrollment.

6.4 Screen Failures

Screen failures are defined as participants who consent to participate in the clinical study but are not subsequently randomized. A minimal set of screen failure information is required to ensure transparent reporting of screen failure participants to meet the Consolidated Standards of Reporting Trials (CONSORT) publishing requirements and to respond to queries from regulatory authorities. Minimal information includes demography, screen failure details, eligibility criteria, and any AEs or SAEs meeting reporting requirements as outlined in the entry guidelines.

6.5 Participant Replacement Strategy

A participant who discontinues from study treatment or withdraws from the study will not be replaced.

7. Treatments

Study treatment is defined as any investigational treatment(s), marketed product(s), placebo, or medical device(s) intended to be administered to a study participant according to the study protocol.

Clinical supplies [study treatment(s) provided by MSD] will be packaged to support enrollment. Clinical supplies will be affixed with a clinical label in accordance with regulatory requirements.

7.1 Treatments Administered

The study treatments to be used in this trial are outlined below in [Table 2](#).

Table 2 Study Treatments

Study Treatment Name	Dosage Formulation	Unit Dose Strength(s)	Dosage Level	Route of Administration	Sourcing
Pembrolizumab	Solution for IV infusion	25 mg/mL	200 mg Q3W Day 1 of each cycle for up to 35 cycles	IV infusion	Provided centrally
Epacadostat or Epacadostat Placebo	Tablet	100 mg	100 mg BID continuously for up to 35 cycles	Oral	Provided centrally
Epacadostat or Epacadostat Placebo	Tablet	25 mg	25 mg or 50 mg* BID continuously for up to 35 cycles	Oral	Provided centrally

*Epacadostat or matching placebo may be reduced to 50 mg BID (Level -1) or 25 mg BID (Level -2) to mitigate immune-related AEs (irAEs), if indicated in [Table 3](#).

Abbreviations: BID = twice daily; IV = intravenous; Q3W = every 3 weeks.

All placebos were created by the Sponsor to match the active product.

All products indicated in [Table 2](#) will be provided centrally by MSD or locally by the trial site, subsidiary, or designee, depending on local country operational or regulatory requirements. Every attempt should be made to source these supplies from a single lot/batch number.

Refer to Section 9.1.9 for details regarding administration of the study treatment.

As of Amendment 04, participants who continue study treatment after unblinding will no longer be dispensed epacadostat placebo.

7.2 Dose Modification (Escalation/Titration/Other)

7.2.1 Dose Modification

Dose modification and toxicity management for immune-related AEs (irAEs) associated with pembrolizumab and/or epacadostat or matching placebo should be managed as follows.

AEs associated with pembrolizumab and epacadostat exposure may represent an immunologic etiology. These irAEs may occur shortly after the first dose or several months after the last dose of treatment and may affect more than one body system simultaneously. Therefore, early recognition and initiation of treatment is critical to reduce complications. Based on existing clinical trial data, most irAEs were reversible and could be managed with interruptions of pembrolizumab, administration of corticosteroids and/or other supportive care. For suspected irAEs, ensure adequate evaluation to confirm etiology or exclude other causes. Additional procedures or tests such as bronchoscopy, endoscopy, skin biopsy may be included as part of the evaluation. Based on the severity of irAEs, withhold or permanently discontinue pembrolizumab and epacadostat/matching placebo and administer corticosteroids.

Table 3 summarizes the irAE dose modification actions for pembrolizumab and epacadostat/matching placebo. Of note, participants who require dose reduction of epacadostat/matching placebo due to AEs will remain at the lower dose, summarized in Table 4. Re-escalation of epacadostat or matching placebo is not permitted.

In cases where pembrolizumab dosing is held, dosing for epacadostat/matching placebo must also be held until pembrolizumab may resume. Participants are allowed, however, to receive pembrolizumab monotherapy at the Investigator's discretion upon improvement of the irAE to Grade 0 or 1, unless discontinuation of both study treatments is specified in Table 3 (eg, if the toxicity was considered related to the combination therapy and not pembrolizumab monotherapy).

Except in cases of emergency, it is recommended that the Investigator consult with the medical monitor (or other representative of MSD) before temporarily interrupting therapy for reasons other than protocol-mandated medication hold.

Table 3 Dose Modification and Toxicity Management Guidelines for Pembrolizumab and Epacadostat or Matching Placebo

Immune-related AEs	Toxicity Grade or Conditions (CTCAEv4.0)	Study Medication	Action Taken with Study Medication	irAE Management with Corticosteroid and/or Other Therapies	Monitor and Follow-up
Pneumonitis	Grade 2	Pembrolizumab	Withhold until Grade 0-1	
 Administer corticosteroids (initial dose of 1-2 mg/kg prednisone or equivalent) followed by taper 	
 Monitor participants for signs and symptoms of pneumonitis Evaluate participants with suspected pneumonitis with radiographic imaging and initiate corticosteroid treatment Add prophylactic antibiotics for opportunistic infections
		Epacadostat or matching placebo	Withhold until Grade 0-1 Once resolved to Grade 0-1, may restart: Related: Reduce by 1 dose level. Not Related: Same dose level.		
	Grade 3 or 4, or recurrent Grade 2	Pembrolizumab	Permanently discontinue		
		Epacadostat or matching placebo	Permanently discontinue		

Immune-related AEs	Toxicity Grade or Conditions (CTCAEv4.0)	Study Medication	Action Taken with Study Medication	irAE Management with Corticosteroid and/or Other Therapies	Monitor and Follow-up
Diarrhea / colitis	Grade 2 or 3	Pembrolizumab	Withhold until Grade 0-1	
 Administer corticosteroids (initial dose of 1-2 mg/kg prednisone or equivalent) followed by taper 	
 Monitor participants for signs and symptoms of enterocolitis (ie, diarrhea, abdominal pain, blood or mucus in stool with or without fever) and of bowel perforation (ie, peritoneal signs and ileus). Participants with \geqGrade 2 diarrhea suspecting colitis should consider GI consultation and performing endoscopy to rule out colitis. Participants with diarrhea/colitis should be advised to drink liberal quantities of clear fluids. If sufficient oral fluid intake is not feasible, fluid and electrolytes should be substituted via IV infusion.
		Epacadostat or matching placebo	Withhold until Grade 0-1 Once resolved to Grade 0-1, may restart: Related: Reduce by 1 dose level. Not Related: Same dose level.		
	Grade 4 or recurrent Grade 3	Pembrolizumab	Permanently discontinue		
		Epacadostat or matching placebo	Permanently discontinue		

Immune-related AEs	Toxicity Grade or Conditions (CTCAEv4.0)	Study Medication	Action Taken with Study Medication	irAE Management with Corticosteroid and/or Other Therapies	Monitor and Follow-up
AST / ALT Elevation or Increased Bilirubin	Grade 2	Pembrolizumab	Withhold until Grade 0-1	
 Administer corticosteroids (initial dose of 0.5-1 mg/kg prednisone or equivalent) followed by taper 	
 Monitor with liver function tests (consider weekly or more frequently until liver enzyme value returns to baseline or is stable).
		Epacadostat or matching placebo	Withhold until Grade 0-1 Once resolved to Grade 0-1, may restart: Related: Reduce by 1 dose level. Not Related: Same dose level.		
	Grade 3 or 4	Pembrolizumab	Permanently discontinue	
 Administer corticosteroids (initial dose of 1-2 mg/kg prednisone or equivalent) followed by taper 	
		Epacadostat or matching placebo	Permanently discontinue		
Type 1 diabetes mellitus (T1DM) or Hyperglycemia*	Newly onset T1DM or Grade 3 or 4 hyperglycemia associated with evidence of β -cell failure	Pembrolizumab	Withhold until Grade 0-1	
 Initiate insulin replacement therapy for participants with T1DM Administer anti-hyperglycemic in participants with hyperglycemia 	
 Monitor participants for hyperglycemia or other signs and symptoms of diabetes.
		Epacadostat or matching placebo	Withhold until Grade 0-1 Once resolved to Grade 0-1, may restart: Related: Reduce by 1 dose level. Not Related: Same dose level.		

Immune-related AEs	Toxicity Grade or Conditions (CTCAEv4.0)	Study Medication	Action Taken with Study Medication	irAE Management with Corticosteroid and/or Other Therapies	Monitor and Follow-up
Hypophysitis	Grade 2	Pembrolizumab	Withhold until Grade 0-1	
 Administer corticosteroids and initiate hormonal replacements as clinically indicated. 	
 Monitor for signs and symptoms of hypophysitis (including hypopituitarism and adrenal insufficiency)
		Epacadostat or matching placebo	Withhold until Grade 0-1 Once resolved to Grade 0-1, may restart: Related: Reduce by 1 dose level. Not Related: Same dose level.		
	Grade 3 or 4	Pembrolizumab	Withhold until Grade 0-1 or permanently discontinue ^b		
		Epacadostat or matching placebo	Withhold until Grade 0-1 or permanently discontinue ^b Once resolved to Grade 0-1, may restart: Related: Reduce by 1 dose level. Not Related: Same dose level.		

Immune-related AEs	Toxicity Grade or Conditions (CTCAEv4.0)	Study Medication	Action Taken with Study Medication	irAE Management with Corticosteroid and/or Other Therapies	Monitor and Follow-up
Hyperthyroidism ^a	Grade 2	Pembrolizumab	Continue	
 Treat with non-selective beta-blockers (eg, propranolol) or thionamides as appropriate 	
 Monitor for signs and symptoms of thyroid disorders.
		Epacadostat or matching placebo	Continue		
	Grade 3 or 4	Pembrolizumab	Withhold until Grade 0-1 or permanently discontinue ^b		
		Epacadostat or matching placebo	Withhold until Grade 0-1 or permanently discontinue ^b Once resolved to Grade 0-1, may restart: Related: Reduce by 1 dose level. Not Related: Same dose level.		
Hypothyroidism ^a	Grade 2-4	Pembrolizumab	Continue	
 Initiate thyroid replacement hormones (eg, levothyroxine or liothyronine) per standard of care 	
 Monitor for signs and symptoms of thyroid disorders.
		Epacadostat or matching placebo	Continue		
Nephritis and Renal Dysfunction	Grade 2	Pembrolizumab	Withhold until Grade 0-1	
 Administer corticosteroids (prednisone 1-2 mg/kg or equivalent) followed by taper. 	
 Monitor changes of renal function
		Epacadostat or matching placebo	Withhold until Grade 0-1 Once resolved to Grade 0-1, may restart: Related: Reduce by 1 dose level. Not Related: Same dose level.		
	Grade 3 or 4	Pembrolizumab	Permanently discontinue		
		Epacadostat or matching placebo	Permanently discontinue		

Immune-related AEs	Toxicity Grade or Conditions (CTCAEv4.0)	Study Medication	Action Taken with Study Medication	irAE Management with Corticosteroid and/or Other Therapies	Monitor and Follow-up
Myocarditis	Grade 1 or 2	Pembrolizumab	Withhold until Grade 0	
 Based on severity of AE administer corticosteroids 	
 Ensure adequate evaluation to confirm etiology and/or exclude other causes
		Epacadostat or matching placebo	Withhold until Grade 0		
	Grade 3 or 4	Pembrolizumab	Permanently discontinue		
		Epacadostat or matching placebo	Permanently discontinue		
Rash	Grade 1 or 2	Pembrolizumab	Continue	
 Manage with topical steroids with or without drug interruption. 	
 If toxicity does not resolve within 12 weeks of last dose, or cannot taper below 10 mg or less of prednisone or equivalent within 12 weeks, must permanently discontinue. Restart epacadostat at same dose if rash is mild and assessed as Grade 3 based only on body surface area and resolves without oral steroids. If oral steroids are required, or rash is severe, decrease by 1 dose level once resolved to Grade 0-1.
		Epacadostat or matching placebo	Continue		
	Grade 3 ^c	Pembrolizumab	Withhold until Grade 0-1	
 Administer corticosteroids (initial dose of 1-2 mg/kg prednisone or equivalent) followed by taper. 	
		Epacadostat or matching placebo	Withhold until Grade 0-1 Once resolved to Grade 0-1, may restart: Related: Reduce by 1 dose level. Not Related: Same dose level.		

Immune-related AEs	Toxicity Grade or Conditions (CTCAEv4.0)	Study Medication	Action Taken with Study Medication	irAE Management with Corticosteroid and/or Other Therapies	Monitor and Follow-up
	Grade 4	Pembrolizumab	Permanently discontinue	
 Administer corticosteroids (initial dose of 1-2 mg/kg prednisone or equivalent) followed by taper. 	
		Epacadostat or matching placebo	Permanently discontinue		
Asymptomatic Amylase or Lipase Increased	Grade 3	Pembrolizumab	May continue treatment with MSD Clinical Director approval		
 Permanently discontinue if clinical signs and symptoms of pancreatitis develop (abdominal pain, nausea, vomiting). If toxicity does not resolve within 12 weeks of last dose after an interruption, must permanently discontinue unless approved by the medical monitor to continue. If Grade 4 lipase/amylase elevation is asymptomatic and abdominal imaging suggests no pathology, study drug administration dosing may continue (with or without dose reduction) with medical monitor approval.
		Epacadostat or matching placebo	May continue treatment with MSD Clinical Director approval		
	Grade 4	Pembrolizumab	Withhold until toxicity resolves to Grade 0-1		
		Epacadostat or matching placebo	Withhold until toxicity resolves to Grade 0-1 Once resolved to Grade 0-1, may restart: Related: Reduce by 1 dose level. Not Related: Same dose level.		

Immune-related AEs	Toxicity Grade or Conditions (CTCAEv4.0)	Study Medication	Action Taken with Study Medication	irAE Management with Corticosteroid and/or Other Therapies	Monitor and Follow-up
All Other Immune-related AEs	Intolerable/ persistent Grade 2	Pembrolizumab	Withhold until Grade 0-1	
 Based on severity of AE administer corticosteroids 	
 Ensure adequate evaluation to confirm etiology or exclude other causes
		Epacadostat or matching placebo	Withhold until Grade 0-1 Once resolved to Grade 0-1, may restart: Related: Reduce by 1 dose level. Not Related: Same dose level.		
	Grade 3	Pembrolizumab	Withhold until Grade 0-1, or discontinue based on the type of event. Events that require discontinuation include and not limited to: Guillain-Barre Syndrome, encephalitis		
		Epacadostat or matching placebo	Withhold until Grade 0-1 Once resolved to Grade 0-1, may restart: Related: Reduce by 1 dose level. Not Related: Same dose level. Events that require discontinuation include and not limited to: Guillain-Barre Syndrome, encephalitis		
	Grade 4 or recurrent Grade 3	Pembrolizumab	Permanently discontinue		
		Epacadostat or matching placebo	Permanently discontinue		

Immune-related AEs	Toxicity Grade or Conditions (CTCAEv4.0)	Study Medication	Action Taken with Study Medication	irAE Management with Corticosteroid and/or Other Therapies	Monitor and Follow-up

General Instructions:
 
 1. Corticosteroid taper should be initiated upon AE improving to Grade 1 or less and continue to taper over at least 4 weeks. 2. For situations where pembrolizumab and epacadostat/placebo have been withheld, pembrolizumab and epacadostat/placebo can be resumed after AE has been reduced to Grade 1 or 0 and corticosteroid has been tapered. Pembrolizumab and epacadostat/placebo should be permanently discontinued if AE does not resolve within 12 weeks of last dose or corticosteroids cannot be reduced to ≤ 10 mg prednisone or equivalent per day within 12 weeks. 3. For severe and life-threatening irAEs, IV corticosteroid should be initiated first followed by oral steroid. Other immunosuppressive treatment should be initiated if irAEs cannot be controlled by corticosteroids. 4. If the same AE that required epacadostat dose reductions to dose level -2 re-occurs, regardless of the causality to epacadostat, epacadostat should be discontinued. If a participant who is being treated at dose level -2 has a different Grade ≥ 3 AE that is considered unrelated to epacadostat by the investigator, the participant may resume study treatment at dose level -2 after discussion with the study medical monitor. 
NOTES:
 
 a. For participants with Grade 3 or 4 immune-related endocrinopathy where withholding of pembrolizumab and epacadostat/placebo is required, pembrolizumab and epacadostat/placebo may be resumed when AE resolves to \leq Grade 2 and is controlled with hormonal replacement therapy or achieved metabolic control (in case of T1DM) b. Withhold OR permanently discontinue pembrolizumab + epacadostat/placebo at the discretion of the Investigator. c. Participants with Grade 3 rash in the absence of desquamation, no mucosal involvement, does not require systemic steroids, and resolves to Grade 1 within 14 days does not have to hold study medication 
Abbreviations: AEs = adverse events; ALT (SGPT) = alanine aminotransferase (serum glutamic pyruvic transaminase); AST (SGOT) = aspartate aminotransferase (serum glutamic oxaloacetic transaminase); CTCAE = Common Terminology Criteria for Adverse Events; IV = intravenous; irAE = infusion-related adverse events; T1DM = Type 1 diabetes mellitus
					

When indicated by Table 3 to mitigate irAEs, the dose of epacadostat or matching placebo must be reduced using the dosing levels outlined in Table 4. Once reduced, re-escalation of epacadostat or matching placebo is not permitted.

Table 4 Dose Level Adjustments for Epacadostat or Matching Placebo

Dose of Epacadostat or Matching Placebo	Dose Level -1	Dose Level -2
	First Reduction of Epacadostat or Placebo	Second Reduction of Epacadostat or Placebo
100 mg BID	50 mg BID	25 mg BID

Abbreviations: BID = twice daily.

Dose Level -2 is the lowest dose of epacadostat in this protocol. Refer to the general instructions in Table 3 for guidance regarding the re-occurrence of an AE when a participant has had their epacadostat dose reduced to dose level -2.

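### For Grade 2 myocarditis that improves to Grade 1, the Table 3 row keeps both drugs on hold until Grade 0, while General Instruction 2, and on one reading Section 7.2.1, permit restart at Grade 1

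*Combined protocol and SAP*

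**What the plan says.** Three texts in Section 7.2.1 of the combined protocol and SAP bear on restarting treatment after a hold for myocarditis.

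- **Table 3, myocarditis row.** For the lower grades the entry reads "Myocarditis Grade 1 or 2 Pembrolizumab Withhold until Grade 0", and the epacadostat/placebo line sets the same limit. For Grade 3 or 4, both drugs are permanently discontinued.
- **Table 3, General Instruction 2.** Where both drugs have been withheld, "pembrolizumab and epacadostat/placebo can be resumed after AE has been reduced to Grade 1 or 0 and corticosteroid has been tapered". No event is excepted from this threshold. The instruction goes on to require permanent discontinuation if the event has not resolved, or the steroid dose cannot be brought low enough, within 12 weeks.
- **Body text before Table 3.** Epacadostat/placebo must be held whenever pembrolizumab is held. The next sentence then says: "Participants are allowed, however, to receive pembrolizumab monotherapy at the Investigator's discretion upon improvement of the irAE to Grade 0 or 1". Its stated limit is "unless discontinuation of both study treatments is specified in Table 3".

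Appendix 4 (assessment of causality, rechallenge) adds a separate safeguard. The MSD Clinical Director must approve in advance a rechallenge planned after a serious event that the study treatment may have caused, or one in which re-exposure carries significant added risk.

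**The concern.** The row sets a stricter restart grade for myocarditis than the general rules around it, but those rules do not acknowledge the difference. A site that applies General Instruction 2 to a participant whose myocarditis has fallen from Grade 2 to Grade 1 would find that dosing can resume after the taper. A site that applies the row would find that it cannot.

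What is at stake is participant safety. The row counts Grade 1 myocarditis as a reason to withhold, so the general text permits dosing at a grade where the row requires a hold. For a participant who stays at Grade 1, the row leads to continued withholding and then to the 12-week discontinuation provisions. The general rules could lead to renewed dosing.

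The question remains live although enrollment has stopped. Participants who benefit may continue for up to 35 cycles (Section 5.1), and those who qualify may receive up to 17 more in the Second Course Phase (Section 7.2.2).

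**Working it through.** The plan gives no figure to reproduce here, and no formula applies. The check is to put one case to each text: Grade 2 myocarditis, both drugs withheld, event now at Grade 1.

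| Text | Restart threshold | Other condition | Answer at Grade 1 |
|---|---|---|---|
| Table 3, myocarditis row | Grade 0 | None stated | Keep holding both drugs |
| General Instruction 2 | Grade 1 or 0 | Steroid tapered | Both drugs can be resumed |
| Section 7.2.1 body text | Grade 0 or 1 | Investigator's discretion | Pembrolizumab alone may be given, on one reading |

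**Step 1. Do the extra conditions remove the difference?** No. Once the taper is complete and the investigator wishes to restart, both conditions are met and the grade thresholds still differ.

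**Step 2. Does the stated exception cover the case?** The exception in the body text applies where Table 3 requires discontinuation of both treatments. For myocarditis that is Grade 3 or 4. At Grade 1 or 2 the table says to withhold, so the exception is not triggered. General Instruction 2 has no event-specific exception to its grade threshold.

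**Step 3. Does any text give the row priority?** None was found. The body text describes Table 3 as a summary of the dose modification actions and does not say which text governs when the two differ.

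**Step 4. How many cases are affected?**
- Grade 3 or 4 is not affected, because treatment stops permanently.
- Improvement to Grade 0 is not affected, because all three texts then allow restart, subject to their other conditions.
- Onset at Grade 1 is not clearly affected, because both general rules speak of an event that has improved or been reduced.
- This leaves Grade 2 improving to Grade 1.

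**Step 5. Is the myocarditis limit unusual?** By row wording, Table 3 has 13 entries that hold pembrolizumab:
- Grade 2 entries: pneumonitis, liver tests, hypophysitis, nephritis, all other events (5).
- Diarrhea/colitis Grade 2 or 3 (1).
- Type 1 diabetes/hyperglycemia (1).
- Grade 3 or 4 entries: hypophysitis, hyperthyroidism (2).
- Myocarditis Grade 1 or 2 (1).
- Rash Grade 3 (1).
- Amylase/lipase Grade 4 (1).
- All other events Grade 3 (1).

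The sum is 5 + 1 + 1 + 2 + 1 + 1 + 1 + 1 = 13. Only the myocarditis entry sets Grade 0. The only other row that lists Grade 1, rash, says to continue treatment. The stricter limit therefore looks deliberate.

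The count describes row wording only. Note a lets Grade 3 or 4 endocrine events restart at Grade 2 or lower when controlled, note c exempts some Grade 3 rash from the hold, and asymptomatic Grade 4 amylase or lipase elevation may continue with approval. It would be wrong to say that the other 12 entries all follow a plain Grade 0-1 rule.

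**The case against.** The strongest reply is that the specific row already gives the answer. A participant at Grade 1 is still inside a row whose trigger is Grade 1 or 2. The other two texts are permissive, so an investigator who holds until Grade 0 breaches nothing, while one who restarts at Grade 1 breaches the row. This stands, and it rules out two stronger readings that a reader might infer: that the protocol requires restart at Grade 1, and that no course of action complies with every text. It does not make the texts consistent, because the permission in General Instruction 2 still covers this case.

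Second, the sentence in Section 7.2.1 may have another purpose. It follows the rule that epacadostat is held whenever pembrolizumab is held, and its example concerns toxicity attributed to the combination and not to pembrolizumab alone. It can be read as leave to drop epacadostat, with no new threshold for pembrolizumab. That reading is reasonable, so the body text is the weaker half of the conflict. General Instruction 2 is unaffected by it.

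Third, one might argue that a departure from Grade 0-1 needs a lettered note, as in note a ("For participants with Grade 3 or 4 immune-related endocrinopathy where withholding of pembrolizumab and epacadostat/placebo is required"), and that its absence for myocarditis favors the general rule. This is weak. Note a relaxes what the endocrine rows say, whereas the stricter myocarditis limit is written in the row itself.

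Fourth, the advance approval in Appendix 4 could catch a restart during ongoing myocarditis. This reduces the risk. It does not settle the rule: Grade 2 myocarditis need not meet the definition of serious, whether re-exposure carries significant added risk is a judgement, and the approval clause refers back to the same dose modification guidelines.

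**Conclusion.** The inconsistency is real and narrow. For Grade 2 myocarditis that has improved to Grade 1, the row requires both drugs to stay on hold. General Instruction 2 says both can be resumed after the taper, and Section 7.2.1 can be read as allowing pembrolizumab alone. No text exempts myocarditis or gives the row priority.

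The conclusion rests on the wording alone. A reader might infer that the general text removes the protection in the row. The documents support only that it permits an exception to it: the row still stands, holding until Grade 0 satisfies every text, and Appendix 4 requires advance approval for some rechallenges. A reader might also want an expected number of cases or of doses given at Grade 1. The documents supply no myocarditis rate and no timing from which either could be derived, so none is offered. Nor can it be said how investigators would in fact restart.

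The ORR estimate, its Clopper-Pearson interval and Table 12 are unaffected. This is a point about the clarity of a safety rule for a rare event.

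**What to change.** Make two insertions.

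1. In the Section 7.2.1 sentence on pembrolizumab monotherapy, after *Grade 0 or 1*, add *(Grade 0 for myocarditis)*.
2. In Table 3, General Instruction 2, after *Grade 1 or 0*, add *(Grade 0 for myocarditis)*.

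Both use the threshold already in the myocarditis row. No clinical limit is introduced or loosened, and no other event is touched. The cost is one short parenthesis in each of two places, with no new data, visits, procedures or analyses.
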